4.2. HYPOTHESES AND PARAMETER ESTIMATES

4.2.1. PRIMARY HYPOTHESIS

- If all ESBL-E-carriers are identified, CI will not reduce ESBL-E incidence densities of ESBL-E-acquisition among patients in medical and surgical wards when compared to SP

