Primary Hypothesis and Outcome	If all ESBL-E-carriers are identified through universal surveillance screening, Contact Isolation (CI) will not reduce incidence densities of ESBL-E-acquisition among patients in medical and surgical wards when compared to SP. The primary outcome is the ESBL-E acquisition rate per 1,000 patient days. Acquisition of ESBL-E-carriage is defined as recovery of ESBL-E isolates from clinical and/or rectal/perianal/stool screening specimens >3 days after admission (admission day = day 1) from patients with negative admission screening results. If a patient is discharged from the ward and re-admitted to the ward on the same or the following day, then the discharge will be ignored in the primary analysis. If the readmission occurs later, the patient will be treated as a new case.
Secondary Hypotheses	
 1. Healthcare workers (HCWs) will not practice HH more frequently during contact with known ESBL-E-carriers in CI than in SP 2. HCWs will practice HH more frequently during contact with known ESBL-E-carriers than with patients not known to be ESBL-E-carriers
Secondary Outcomes	The trial will assess the efficacy of the CI strategy in reducing the incidence density of colonization with ESBL-E by the methods described above. In addition, the trial will evaluate the efficacy of the CI strategy in reducing the cumulative incidence of ESBL-E infections as determined by laboratory-based surveillance of clinical culture results. The trial will evaluate the frequency of hand hygiene and the use of gloves and gowns by HCWs, as assessed by bedside observations of a trained monitor. The antibiotic use will be analysed for all patients in defined daily doses (DDD) preferably weekly/at least monthly. In a subset of ESBL-E-patients antibiotic use will also be analysed at patient level in days of therapy (DOT). The trial will evaluate the consumption of alcohol-based handrub (ABHR) per patient days to evaluate differences between ESBL-E-carriers and Non-ESBL-E-patients as well as differences between the two IC strategies. Because the interventions involve minimal risk, no specific safety measures will be made.
Study Design	The study is a two-arm, cluster-(Non-ICU) randomized, controlled study (cRCT) of two IC strategies with cross-over design, which will be performed in different European countries. Randomization will be performed at the ward level. Primary analyses will be performed at the ward level.

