Study population	
Inclusion criteria	
 • Adult medical and surgical Non-ICUs with approval from the medical director and head nurses, approximately 1000 admissions/year and an expected non-varying average length of stay for the 2 intervention periods • Ability to implement a universal ESBL-E admission and discharge screening • Written approval of the study from the local Institutional Review Board (IRB)
Exclusion criteria	
 • Transplant and paediatric wards, ICUs • Wards planning to enrol subjects in a study of an investigational agent administered for the purpose of eradicating or preventing colonization with ESBL-E or to reduce the likelihood of transmission of these bacteria
Sample Size	
Assuming an average new acquisition of ESBL-producers in hospital of 0.8/100 patients on non-ICUs, a design effect (DE) of 2.9 and a corresponding intracluster correlation coefficient (ICC) of 0.003, 20 wards with 36.788 included patients (18.394 per study arm) will have the a power of at least 80% to detect at least a 50% reduction in risk in wards during CI vs. SP period with a Type I error rate of 0.05 for a 2-sided test.

Randomization	
Randomization will occur at the ward level with a block size of 2. Groups of two consecutive wards will be randomized to one of the two arms.

Data Analyses	
For the primary efficacy analysis, incidence density of nosocomial ESBL-E acquisition will be computed at hospital level and ward level. A one degree of freedom test from an analysis of multivariate model will be used to test for differences in mean incidence density ratios of ESBL-E acquisition between the two strategies. This will be calculated by Poisson or negative-binomial regression analysis with monthly aggregated data using Generalized Estimating Equation (GEE) models with adjustment by several confounding parameters besides cluster effects by ward and hospital.

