4. OBJECTIVES AND HYPOTHESES

4.1. OBJECTIVES

4.1.1. PRIMARY OBJECTIVE

- To determine the additional effects of CI compared to a SP strategy on the incidence density of nosocomial ESBL-E-acquisition among hospitalized patients in adult Non-ICU wards in hospitals with universal ESBL-E admission and discharge screening

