4.2.2. SECONDARY HYPOTHESES

- HCWs will not practice hand hygiene (HH) more frequently during contact with known ESBL-E-carriers in CI than in SP
- HCWs will practice HH more frequently during contact with known ESBL-E-carriers than with patients not known to be ESBL-E-carriers

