9. STATISTICAL ANALYSIS

9.1. SAMPLE SIZE

20 wards in Europe will participate in this cluster-randomized, multi-center, crossover-design study.

Calculations are based upon the following assumptions:

- For this study, the average incidence of nosocomial acquisition of ESBL-E-producing *Enterobacteriaceae* determined using regular surveillance cultures is assumed to be at least 0.8 per 100 patients in Non-ICUs, a ratio of 1:1 for exposed (CI) and unexposed (SP) patients, $\alpha=0.05$, and $\beta = 0.80$. This assumption is considered to be reasonable because the incidence of MDRO colonization determined by regular surveillance cultures is substantially higher than MDRO incidence determined by cultures obtained for clinical indications only^{29, 30}.
- Because CI does have side effects for the patients and is both resource- and time-intensive and all ESBL-E-patients are identified by routine surveillance cultures, the study is powered to detect a 50% reduction in the incidence of ESBL-E-acquisition compared to the SP strategy.
- Based on these preconditions, 12,686 patients will be observed in the trial, 6,343 in each intervention phase.
- In order to determine the number of cases for a cluster-randomized study that correlates to the power of the number of cases determined by randomization at the individual level, this has to be multiplied with a design-effect factor: $DE=1 + (n-1)*p$. N is the number of individuals per cluster, and p is the intracluster correlation coefficient (ICC). The ICC is a measure for the similarity of the data of the cluster. It describes the similarity of cluster data by comparing the variance within clusters with the variance between clusters. According to the authors' knowledge, there is no study which describes inter- and intra-cluster variance in this setting. In various studies with dichotomous outcome, the design effect (DE) varies between 1.0 and 3.0³¹⁻³⁴.
- We assume a conservative design effect (DE) of 2.9. This results in a necessary number of cases of 36,788 patients, or 18,394 per study arm. With a DE of 2.9 in an individual randomization, 20 clusters and 635 patients per cluster, the corresponding ICC is 0.003. This assumed ICC is justified because we assume only a small variance between clusters.

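### The primary hypothesis predicts no effect of contact isolation (CI), but the test and sample size are those of a two-sided superiority trial, so a non-significant result cannot establish it

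*Protocol*

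**What the plan says.** The primary hypothesis is worded as absence of effect, both in Section 4.2.1 ("CI will not reduce ESBL-E incidence densities of ESBL-E-acquisition among patients in medical and surgical wards when compared to SP") and in the Synopsis ("Contact Isolation (CI) will not reduce incidence densities of ESBL-E-acquisition among patients in medical and surgical wards when compared to SP"). The first secondary hypothesis in Section 4.2.2 has the same form: "HCWs will not practice hand hygiene (HH) more frequently during contact with known ESBL-E-carriers in CI than in SP". The second secondary hypothesis, next to it, is a positive prediction about hand hygiene with known carriers.

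The primary objective in Section 4.1.1 is neutral: "To determine the additional effects of CI compared to a SP strategy on the incidence density of nosocomial ESBL-E-acquisition".

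The sizing is for detecting a difference. Section 9.1 says "the study is powered to detect a 50% reduction in the incidence of ESBL-E-acquisition compared to the SP strategy". The Synopsis gives "power of at least 80% to detect at least a 50% reduction in risk in wards during CI vs. SP period"; its significance level is 0.05, two-sided. Its data analysis entry plans a one-degree-of-freedom test for a difference between strategies. The Synopsis and Sections 9.1 and 9.2.3 give no margin, no confidence-interval rule and no statement of what a non-significant result would mean.

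**The concern.** The hypothesis, test and sample size do not fit together. A difference test can reject equality; it cannot show that equality holds. If the investigators expect no reduction and run only a difference test, the single outcome that could look like support is failure to reject. That outcome becomes more likely as the trial becomes less precise, for example with fewer acquisitions than assumed, incomplete screening or weak adherence to isolation.

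At stake is the headline conclusion. Without a stated rule, a reader could take a non-significant result as evidence that isolation adds nothing, even though the interval may be compatible with a sizeable reduction.

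**Working it through.** **Inputs.** Control risk: Section 9.1 states that it "is assumed to be at least 0.8 per 100 patients in Non-ICUs". Target: 50% reduction, so 0.8% against 0.4%. Two-sided alpha 0.05, power 80%, allocation 1:1. Stated size: 6,343 per strategy before the design effect (DE) and 18,394 per arm after DE 2.9. Section 9.1 quotes a DE range of 1.0 to 3.0 from other studies, so 2.9, 2.0 and 1.0 are shown.

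**Step 1: reproduce the plan's figure.** With p1 = 0.008, p2 = 0.004 and mean p = 0.006:

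n0 = [1.96·√(2p(1−p)) + 0.8416·√(p1(1−p1) + p2(1−p2))]² / (p1−p2)² = 5,851

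With continuity correction: n = (n0/4)·[1 + √(1 + 4/(n0·0.004))]² = 6,341, against 6,343 stated. One-sided versions give 4,609 (5,096 with correction) and do not match. Then 12,686 × 2.9 = 36,789, against 36,788 stated. The plan's number is therefore a two-sided superiority calculation.

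**Step 2: precision if CI does nothing.** Events per arm = 18,394 × 0.008 = 147. SE(log IDR) = √(2·DE/147). Interval around an observed IDR of 1.00 = exp(±1.96·SE).

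**Step 3: chance of missing a true 30% reduction.** At IDR r = 0.7, SE = √(DE·(1/147 + 1/(147·r))) and power = Φ(−ln r/SE − 1.96). At DE 2.9: SE = 0.219, power = Φ(0.357/0.219 − 1.96) = 37%.

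**Step 4: chance of excluding a reduction when the true IDR is 1.** The lower 95% limit exceeds margin m with probability Φ(−ln m/SE − 1.96), using the SE of step 2. For m = 0.50 at DE 2.9: Φ(0.693/0.199 − 1.96) = 94%.

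| | DE 2.9 | DE 2.0 | DE 1.0 |
|---|---|---|---|
| SE(log IDR) at IDR 1 | 0.199 | 0.165 | 0.117 |
| 95% CI at observed IDR 1.00 | 0.68–1.48 | 0.72–1.38 | 0.80–1.26 |
| True 30% reduction missed | 63% | 50% | 21% |
| Power to exclude 0.50 | 94% | 99% | >99% |
| Power to exclude 0.67 | 52% | 68% | 93% |
| Power to exclude 0.75 | 30% | 41% | 69% |

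The same formulas at DE 2.9 show how observed results would read. An observed 35% reduction is not significant (0.65, CI 0.42 to 1.01). An observed 25% reduction does not exclude the plan's own target effect (0.75, CI 0.49 to 1.14).

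**The case against.** The strongest reply is that, apart from the hypothesis wording, this is a coherent superiority design. The objective is neutral, CI is labelled the intervention and SP the control, and the sample size reproduces as a two-sided test. On that view the hypothesis sentence is simply the null of that test. Section 9.2.3 also plans crude and adjusted incidence-density ratios, so the result is not reduced to a p-value, and detailed reporting rules may sit in a statistical analysis plan that is not at hand.

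The coherence of the rest of the design stands. Reading the sentence as a formal null does not: Section 4.2.2 puts one prediction that something will not happen beside another that something will, so these statements record what the investigators expect to show. A later analysis plan could add a rule, but hypothesis, sizing and test are all fixed in the protocol, and they disagree there.

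Three stronger readings are tempting and not supported:

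- A reader might infer that the protocol will treat p>0.05 as confirmation. It states no such rule.
- A reader might infer that clinically relevant reductions will be missed. The documents do not say that reductions of 20% to 40% are relevant. Section 9.1 justifies only 50%, by the side effects and resource demands of CI, and as an effect to detect rather than the largest that may be dismissed.
- A reader might infer that the trial is too small. On the ratio scale of the primary analysis it is large enough to exclude a halving.

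The objection that DE 2.9 is near the worst case is also fair. It is close to the top of the quoted range and comes from a parallel-cluster formula, although every ward receives both strategies. The table therefore gives the range.

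**Conclusion.** The mismatch is real and should be fixed. The primary hypothesis as worded cannot be established by the planned test, whatever the design effect. The size of the gap does depend on it: around an observed IDR of 1.00, the lower limit runs from 0.68 (DE 2.9) to 0.80 (DE 1.0), so reductions of about 32% and 20% respectively would remain compatible with the data.

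The figures assume a control risk of 0.8 per 100, 18,394 patients per arm, a normal approximation on the log scale, and equal length of stay in both periods (a ward selection condition in Section 5.8), so that the risk ratio and the IDR coincide. A lower acquisition rate would widen the intervals. The sample size, model and conduct of the trial are not in question.

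**What to change.** 1. Restate the primary hypothesis in the Synopsis and Section 4.2.1 to match the design: H0 is IDR (CI:SP) = 1, and the alternative is that CI changes the acquisition rate, tested two-sided at 0.05.
2. Add to Section 9.2.3 that p>0.05 alone is inconclusive and is reported with the 95% CI of the IDR.
3. On the only effect size the plan states, allow the claim that a reduction of 50% or more is excluded only if the lower 95% limit exceeds 0.50 (about 94% power at IDR 1 with DE 2.9).
4. If a claim about smaller reductions is wanted, justify a tighter margin before unblinding and state its power. At DE 2.9 this is about 52% for 0.67 and 30% for 0.75, so the sponsor should know beforehand that such a claim may be out of reach.
5. Reword the first secondary hypothesis as a two-sided comparison of hand hygiene between the strategies, reported with its confidence interval.

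The cost is wording in the protocol and analysis plan, with no added patients or data. The downside for the sponsor is that a non-significant result can no longer be reported as showing that CI has no effect.

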4.2.2. SECONDARY HYPOTHESES

- HCWs will not practice hand hygiene (HH) more frequently during contact with known ESBL-E-carriers in CI than in SP
- HCWs will practice HH more frequently during contact with known ESBL-E-carriers than with patients not known to be ESBL-E-carriers

5. METHODS

[figure not shown]
5.1. STUDY DESIGN

The study is a two-arm, cluster-randomized, controlled study (cRCT) of two IC strategies with cross-over design, which will be performed in 4 European countries to achieve high external validity of study results.

An attempt will be made to identify all intestinal ESBL-E-carriers by active surveillance testing and cultures obtained for clinical indications.

Two IC strategies (CI and SP) will be compared for ESBL-E-positive patients in different units for 12 months each. Because these IC strategies will be implemented as a unit-wide measure, all patients hospitalized in a specific unit will be subjected to the allocated IC strategy of the unit (figure 1). Wards will be assigned to the IC strategy in a random order and will then switch strategies after a wash-out period of one month in the following year.

Figure 1: Study design WP5

The two strategies are as follows:

5.2. STANDARD PRECAUTIONS (SP) (= CONTROL ARM)

For all patients – including known ESBL-E-carriers – SP will be performed. The indications and technique for HH will be consistent with those recommended by the WHO’s “Five Moments”²⁵. Clean gloves and gowns/aprons will be used for all interactions that involve potentially infectious procedures⁷. Non-sterile gloves are considered adequate; non-latex-gloves are used for medical staff and/or patients with latex allergy. Gloves should be changed after contact with

infectious material, such as blood, stool, urine or wound drainage. Gloves should be removed immediately after use and HH should be practiced before touching non-contaminated surfaces or going to another patient. Accordingly, clean gowns/aprons should be donned if contact with patient's blood or body fluids is expected. Gowns should be removed promptly after use and HH should be practiced before touching non-contaminated surfaces or going to another patient. This strategy represents the current standard of care and all patients will be subjected to this IC strategy on wards in the SP phase of the trial.

5.3. CONTACT ISOLATION (CI) (= INTERVENTION ARM)

All patients who are known to be colonized/infected with ESBL-E prior to admission or as a consequence of the surveillance cultures and/or of cultures obtained for clinical indications will be cared for using contact precautions, preferably in a single room or in a shared room with patients who are colonized with the same organism. If isolation in a single room or a shared room with patients colonized with the same organism is impossible, gloves and gowns/aprons will be used for all interactions with the patient or the patient's environment in a shared room. Clean gloves and gowns/aprons will be used for all interactions that involve direct contact with the patient or the patient's environment⁷. Non-sterile gloves are considered adequate; non-latex-gloves are used for medical staff and/or patients with latex allergy. Gloves should be changed after contact with infectious material, such as blood, stool, urine or wound drainage. Gloves should be removed immediately after use and hand hygiene should be practiced before touching non-contaminated surfaces or going to another patient. Clean gowns/aprons should be donned if contact with the patient or with environmental surfaces in the patient's room is expected. Gowns should be removed promptly after use and HH should be practiced before touching non-contaminated surfaces or going to another patient. HH will be performed according to WHO's "Five Moments"²⁵. As the intervention strategy will be implemented as a unit-wide IC measure, all patients known to be colonized/infected with ESBL-E-producing bacteria will be subjected to this IC strategy on wards in the CI phase of the trial.

Both strategies (SP and CI) will be applied in all units for a period of 12 months each with a washout period of one month between the 2 study periods.

5.4. ISOLATION FOR OTHER MULTIDRUG-RESISTANT BACTERIA

In the event that CI is indicated in patients positive for other pathogens (e.g. MRSA, multi drug resistant *Acinetobacter baumannii*, *Clostridium difficile* etc.), it will be implemented according to the hospitals' IC and isolation policies. However, in both periods, patients with known carriage/infection with Carbapenem-resistant *Enterobacteriaceae* will be assigned to strict CI, following widely accepted European guidelines²⁶.

5.5. SURVEILLANCE CULTURES

In both arms of the trial, wards will collect surveillance cultures to identify patients who are colonized with ESBL-E using the same procedures. The results of the surveillance cultures will be reported back to the wards immediately in both arms of the trial.

All patients will be screened at admission (admission day = day 1) to the ward or as soon as possible within 3 days. Repeated surveillance cultures will be obtained for patients staying longer than 7 days on a specific day each week (i.e., every Wednesday, Friday etc.). Patients discharged from the ward will have samples obtained on the day of discharge, if possible, or the day before. Patients readmitted to the ward will be treated as new cases.

The procedures for obtaining and processing swabs are outlined in Section 6.4. (SURVEILLANCE CULTURES).

Surveillance cultures will be obtained by the ward nurses and/or research personnel.

All specimens will be processed by the institutional microbiology laboratories. In all wards, clinicians may order microbiological cultures at any time for clinical indications. All results will be reported as soon as possible to the wards. ESBL-E-isolates will be sent to the microbiologic laboratory of the Hospital Ramon y Cajal in Madrid (SERMAS) for further molecular epidemiologic analysis.

5.6. TRAINING

All IC measures (including SP and HH policies) will be introduced to HCWs by local study personnel at the beginning of each intervention period. An introductory course for local study personnel will include the training of all methods and the monitoring process.

The introductory course will take place at the study sites and will be organized by Charité Berlin.

[figure not shown]
5.7. STUDY PERIODS AND TIMELINE

The study will be divided into a three-month baseline period, a first 12-month intervention phase, a one-month washout period, a second 12-month intervention phase and a three-month post intervention period.

During the baseline and the post-intervention period, only data on nosocomial ESBL-E-acquisition detected by clinical sampling will be collected on the participating wards. In the intervention phases, data on ESBL-E-acquisition detected by active surveillance testing as well as clinical sampling will be collected.

During the one-month washout period, the protocol of the following intervention period will be applied. Only data on nosocomial ESBL-E-acquisition detected by clinical sampling will be collected except for the Follow-up of patients admitted during the preceding period.

Figure 2: Timeline WP5 for Participating Wards

5.8. SELECTION AND WITHDRAWAL OF SITES

The study will be realized in 20 wards in 5 hospitals in 4 European countries (Netherlands, Switzerland, Spain and Germany) during a 31-month period from 08/2013 to 02/2016.

Hospitals with adult medical and surgical wards will be selected for the study.

Because IC strategies will be applied at the ward level, the participation of each unit requires the signed approval of the physician and nursing directors of the ward instead of each patient's approval.

Minimum patient turnover should reach approximately 1000 admissions per year. To have equal conditions in both intervention periods average length of stay should be expected to be non-varying.

Wards that meet any of the following criteria are excluded from the study:

- transplant wards
- paediatric wards

Table 1: Number of hospitals and wards per country

Country	Total number of hospitals	Total number of wards
Netherlands	1	4
Switzerland	1	4
Spain	1	4
Germany	2	8

The medical or nursing directors or the site investigator may withdraw his or her site from the study for any reason at any time.

The study investigators may discontinue the participation of a study site for the following reasons:

- The site does not follow the trial protocol with regard to obtaining the surveillance cultures
- The site does not implement the assigned IC strategy to satisfaction.
- During the trial, the ward enrolls subjects in a study administering an investigational agent for the purpose of controlling, eradicating or preventing colonization with ESBL-E.
- The site's IRB does not provide a waiver for informed consent

In case the protocol is not sufficiently implemented this issue should be discussed with the WP5 partners. They will decide whether replacement of the ward is necessary.

In the event of an unexpected change in antimicrobial resistance epidemiology in a certain ward (e.g. an outbreak), creating a situation in which adherence to protocol can no longer be recommended, the site will temporarily be withdrawn. If withdrawal exceeds three months, the site will be excluded. In the event of the withdrawal or discontinuation of a ward, the R-GNOSIS WP5 partners will decide whether replacement of the ward is necessary.

However, an ITT (intention to treat) analysis will be performed.

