5.9. RANDOMIZATION

Randomization will occur at the ward level. Groups of two consecutive wards will be randomized to one of the two arms.

The investigators will be aware of the assigned IC strategy in order to monitor implementation of each strategy. Data analysts will be unaware of the IC strategy assignment.

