5.10. ENDPOINTS AND OUTCOMES

5.10.1. PRIMARY ENDPOINT

Incidence density of colonization with ESBL-E across the study periods.

- The primary outcome is the nosocomial ESBL-E-acquisition rate per 1,000 patient days. Acquisition of ESBL-E-carriage is defined as recovery of ESBL-E isolates from clinical and/or rectal screening specimens >3 days after hospital admission (admission day = day 1) from patients with negative admission screening results. If a patient is discharged from the ward and re-admitted to the ward on the same or the following day, then the discharge will be ignored in the primary analysis. If the readmission occurs later, the patient will be treated as a new case.

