9.2.3. ANALYSES OF PRIMARY OUTCOMES

The incidence density of ESBL-E-acquisitions in the SP strategy and the CI strategy will be compared in total and at study arm, hospital level and ward level.

In the univariate and multivariable analysis, crude and adjusted incidence-density ratios of ESBL-E-acquisition between the two strategies will be calculated by Poisson or negative-binomial regression analysis with, at best, weekly (if this is impossible at least monthly) aggregated data using Generalized Estimating Equation (GEE) models. Additionally, a Generalized Linear Mixed Model (GLMM) will be used to consider temporary trends in the periods. In total, 480 observation months will be analysed for the 20 wards with 12 observation months each per IC strategy. To analyse 1 degree of freedom in the regression model (e.g. a dichotomous parameter or a continuous parameter), 20 observations are required. The log number of patient days will be treated as offset parameter.

The models will take into account for the clustering effects "hospital" and "ward" and will consider the following parameters: strategy, type and size of ward, type and size of hospital, antibiotic use of different antibiotic groups (DDD/1000 patient days or PDD/100 patients), staff equipment and the burden of ESBL-E at admission (ESBL-E patients on admission per 100 admitted patients), after grouping wards into "higher" or "lower" ESBL-E burden based on median proportion of ESBL-E carriers on admission.

A GLMM model with parameters not on the causal pathway between exposure and outcome and based on expert knowledge and will be considered (i.e. strategy, antibiotic use, staff equipment, burden of ESBL-E on admission, time trend). Parameters with a causal connection

to nosocomial ESBL-E-acquisitions such as AHC and single room use will not be considered in this model.

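### Section 5.8 lets an outbreak, which can itself be a cluster of primary-outcome events, withdraw or exclude a ward, and does not reconcile this with the promised ITT analysis

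*Protocol*

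**What the plan says.** Section 5.8 gives the trigger as "In the event of an unexpected change in antimicrobial resistance epidemiology in a certain ward (e.g. an outbreak", qualified as "creating a situation in which adherence to protocol can no longer be recommended, the site will temporarily be withdrawn". It continues: "If withdrawal exceeds three months, the site will be excluded". For a withdrawn or discontinued ward, "the R-GNOSIS WP5 partners will decide whether replacement of the ward is necessary". The section closes: "However, an ITT (intention to treat) analysis will be performed".

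Three other places bear on this:

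- Section 5.10.1: "The primary outcome is the nosocomial ESBL-E-acquisition rate per 1,000 patient days".
- Section 5.9: "The investigators will be aware of the assigned IC strategy in order to monitor implementation of each strategy". Data analysts are unaware of it.
- Section 9.2.3: "In total, 480 observation months will be analysed for the 20 wards with 12 observation months each per IC strategy".

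Section 5.8 sets no number of cases for an outbreak and does not say who judges that adherence can no longer be recommended. It does not say whether screening and data forms continue during withdrawal, whether those months enter the analysis, or whether an excluded ward keeps its data from the other phase.

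**The concern.** An ESBL-E outbreak on a study ward is a cluster of the acquisitions that the trial counts, so the rule lets the outcome decide which ward-months are observed. The decision is a judgement, taken where the strategy is known, and section 5.5 has screening results reported to the wards at once in both arms.

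If CI reduces acquisition, standard precautions (SP) months will reach any given outbreak level more often than CI months. Losing them lowers the SP rate more than the CI rate and moves the ratio toward 1. That is the direction of the protocol's own primary hypothesis, that CI does not reduce acquisition.

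The closing ITT sentence repairs this only if the data exist. A statistical analysis plan can define analysis sets, but it cannot recover swabs, census counts and patient forms that were never collected. Whether collection continues is for the protocol to fix.

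**Working it through.** **The plan's own figures.** Section 9.2.3: 20 wards x 12 months x 2 strategies = 480 ward-months, 240 per strategy, with none lost. Section 9.1: 988 patients per ward-year and 0.8 acquisitions per 100 patients. Expected SP acquisitions are 0.008 x 988.2 x 20 = 158.1, or 158.1/240 = 0.659 per ward-month and 7.9 per ward-year. With a 50% reduction, CI has 79.1. Full data give a ratio of 79.1/158.1 = 0.50.

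**Assumptions.** The protocol gives no number, size or duration of outbreaks, so the following are assumed. Monthly counts are Poisson around these means, multiplied by a gamma frailty (shape 1 or 0.5) shared within three-month blocks of a ward. A ward is withdrawn when a month has at least 4, 5 or 6 acquisitions. Either the trigger month stays and the next two are lost, or all three are lost.

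| Withdrawal rule | True ratio | Trigger month kept | Trigger month also lost |
|---|---|---|---|
| Same trigger in both phases | 0.50 | about 0.50 to 0.55 | about 0.52 to 0.64 |
| SP phase only | 0.50 | 0.51 to 0.57 | 0.52 to 0.73 |

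The lower end of 0.50 covers the case in which the months after the trigger are independent of it; the bias then vanishes. With the same trigger in both phases and a true ratio of 1.0, the observed ratio is 0.99 to 1.02, which is no shift.

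**Dependence on where withdrawals fall.** Take outbreaks of 5 cases that each remove 3 ward-months, cases included.

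- Four in SP, none in CI, true 0.50: (79.1/240) / ((158.1 - 20)/(240 - 12)) = 0.329/0.606 = 0.54.
- The same, true 1.0: 0.659/0.606 = 1.09.
- Four in each strategy, true 0.50: (79.1 - 20)/(158.1 - 20) = 59.1/138.1 = 0.43, away from 1.

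**Rough cost in power.** The stated 80% power at a ratio of 0.50 implies a standard error of ln 2/2.80 = 0.247 on the log scale. With power = Phi(|ln ratio|/0.247 - 1.96), an observed 0.55 gives Phi(0.46) = 68%, and 0.64 gives Phi(-0.15) = 44%. These are the unfavourable ends of the same-trigger ranges.

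**Replacement.** Sections 5.7 and 5.8 give a 31-month schedule in a 31-month window. Two phases plus washout need 12 + 1 + 12 = 25 months, and 31 - 25 = 6, so a ward starting after month 7 cannot complete both phases.

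**The case against.** The strongest reply is that section 5.8 never says that withdrawn months leave the analysis. The ITT sentence opens with a contrast to the withdrawal sentences, and can be read to mean that a ward may stop following its strategy and still be analysed as randomised. Handling of withdrawn cluster-months is also often left to an analysis plan. The first part stands: the text leaves the matter open, and a reader who infers that the data are certainly lost goes too far. The second part does not help, because the gap is in data collection, and section 5.8 goes beyond temporary withdrawal to exclusion.

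A further objection is that withdrawal follows recognition of an outbreak and nothing deletes acquisitions already recorded. This stands, which makes the column with the trigger month kept the more natural reading and the effect modest. The top of each range also needs strong clustering: 4 acquisitions in one month is about half of the 7.9 expected in a whole SP ward-year.

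Finally, the trigger is any change in resistance epidemiology, not only in ESBL-E, and it is narrowed by the condition on adherence. Both are true. They reduce how often the rule meets the primary outcome but do not prevent it.

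**Conclusion.** The point holds as a conflict within the protocol that carries a risk of bias. Withdrawal can depend on the primary outcome, has no threshold and is open to judgement by staff who know the strategy. The ITT promise and the 480 ward-months cannot both be honoured if outcome collection stops. The likely direction, if CI works, is toward 1. The size rests wholly on the assumed outbreak pattern: about 0.50 to 0.55 for a true 0.50 with the trigger month kept, and about 0.52 to 0.64 with it dropped, under one trigger for both phases.

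Three stronger readings are not supported:

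- A reader might infer that the lost months will be mainly SP months. That is plausible if CI works or if SP is the strategy given up in an outbreak, but no section says so.
- A reader might infer that the ratio could pass 1 and make CI look harmful. That needs a true ratio at or near 1 together with more frequent withdrawal under SP. Equal numbers of withdrawals in both strategies can even move the ratio away from 1.
- A reader might take 'site' to mean a hospital with four wards. The section locates the event in a ward and also speaks of withdrawal of a ward, so this is loose wording.

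**What to change.** Leave the local outbreak response as it is and change only the data rules in section 5.8:

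1. State that admission, weekly and discharge screening, the daily census and Form 3 continue during any withdrawal from the assigned strategy, as far as the ward still agrees to take part.
2. Keep all ward-months and acquisitions in the primary ITT analysis under the strategy assigned for that phase, and record the dates of each departure.
3. Replace the three-month exclusion from the study with a sensitivity analysis that omits outbreak months by one rule, written in advance and identical for both phases.
4. Write 'ward' instead of 'site' throughout the paragraph.
5. Do not let a replacement ward stand in for the withdrawn ward in the primary analysis.

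The change is one of wording, plus continued screening work in the affected months. Months in which a ward departs from its strategy will slightly dilute the contrast, as in any ITT analysis. Section 5.8 lets ward directors and the site investigator withdraw for any reason, so some loss may remain; it should be reported by strategy.
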